2.2 Secondary

- 2.21 To determine the overall survival of patients with advanced biliary tract cancer with mutations in DNA repair genes treated with olaparib.
- 2.22 To determine the progression free survival of patients with advanced biliary tract cancer with mutations in DNA repair genes treated with olaparib
- 2.23 To determine the objective response of patients with advanced biliary tract cancer with mutations in DNA repair genes treated with olaparib.
- 2.2 To assess the duration of response for patients with advanced biliary tract cancer with mutations in DNA repair genes treated with olaparib who experience an objective response.
- 2.25 To assess the frequency and severity of adverse events in advanced biliary tract cancer patients treated with olaparib.

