3.1 Inclusion Criteria

- 3.11 Age ≥ 18 years.
- 3.12 Histological or cytological documentation of metastatic adenocarcinoma of the biliary tract.
- 3.13 Patients with previously identified genetic aberrations that are associated with homologous recombinant repair pathway will be eligible [e.g. somatic mutations in *ATM*, *ATR*, *CHEK2*, *BRCA 1/2*, *RAD51*, *BRIP1*, *PALB2*, *PTEN*, *FANC*, *NBN*, *EMSY*, *MRE11*, *ARID1A*] or germline mutations in the above genes. CLIA-certified assays including commercial tests (Foundation Medicine, Caris, Tempus) will be allowed.
- 3.14 Measurable disease as defined in Section 11.0.
- 3.15 ECOG Performance Status (PS) 0 to 2. (Form is available on the ACCRU web site).
- 3.16 Life expectancy of ≥ 16 weeks per estimation of investigator.
- 3.17 The following laboratory values obtained ≤ 7 days prior to registration.
 - Absolute neutrophil count (ANC) $\geq 1500/\text{mm}^3$
 - Platelet count $\geq 75,000/\text{mm}^3$
 - Hemoglobin ≥ 9.0 g/dL with no blood transfusion in the past 28 days
 - Total bilirubin $\leq 1.5 \times$ upper limit of normal (ULN)
 - Alanine aminotransferase (ALT) and aspartate amino-transferase (AST) $\leq 2.5 \times$ ULN ($\leq 5 \times$ ULN for subjects with liver involvement of their cancer)
 - Serum creatinine $\leq 1.5 \times$ ULN
 - INR/aPTT $\leq 1.5 \times$ ULN

Exception: Patients who are therapeutically treated with anticoagulant agents will be allowed to participate provided that no prior evidence of underlying abnormality in coagulation parameters exists. Close monitoring of at least weekly evaluations will be performed until INR/PTT is stable based on a measurement that is pre-dose as defined by the local standard of care.

 - Alkaline phosphatase limit $\leq 2.5 \times$ ULN ($\leq 5 \times$ ULN for patients with liver involvement of their cancer)
 - Creatinine clearance estimated of ≥ 1 mL/min using the Cockcroft-Gault equation.

Cockcroft-Gault Equation:

Creatinine clearance for males =
$$\frac{(140 - \text{age})(\text{weight in kg})}{(72)(\text{serum creatinine in mg/dL})}$$

Creatinine clearance for females =
$$\frac{(140 - \text{age})(\text{weight in kg})(0.85)}{(72)(\text{serum creatinine in mg/dL})}$$

- 3.18 Negative serum pregnancy test done ≤ 28 days prior to registration and confirmed prior to treatment on day 1, for women of childbearing potential, postmenopausal women or women of childbearing potential with evidence of non-childbearing status.

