- 3.29g Renal failure requiring hemo-or peritoneal dialysis.
- 3.29h Dehydration CTCAE v5.0 grade ≥2.
- 3.29i Substance abuse, medical, psychological or social conditions that may interfere with the patient's participation in the study or evaluation of the study results.
- 3.29j Known hypersensitivity to any of the study drugs, study drug classes, or excipients in the formulation.
- 3.29k Interstitial lung disease with ongoing signs and symptoms at the time of informed consent.
- 3.29l Persistent proteinuria of CTCAE v5.0 Grade 3 or higher (≥ 3.5 g/24 hrs).
- 3.29m Unable to swallow orally administered medications.
- 3.29n Any malabsorption condition and/or patients with gastrointestinal disorders likely to interfere with absorption of the study medication
- 3.29o Unresolved toxicity greater than CTCAE v5.0 Grade 2 attributed to any prior therapy/procedure excluding alopecia and oxaliplatin induced neurotoxicity ≤Grade 2.
- 3.29p Albumin levels <2.5 g/dl.
- 3.29q Any of the following because this study involves an investigational agent whose genotoxic, mutagenic and teratogenic effects on the developing fetus and newborn are unknown.
 - Pregnant women
 - Nursing women
 - Men or women of childbearing potential who are unwilling to employ adequate contraception

NOTE: Women of childbearing potential and their partners, who are sexually active, must agree to the use of TWO highly effective forms of contraception in combination (as described in Appendix V). This should be started from the time of registration and continue throughout the period of taking study treatment and for at least 1 month after last dose of study drug(s), or they must totally/truly abstain from any form of sexual intercourse (as described in Appendix V).

Male patients must use a condom during treatment and for 3 months after the last dose of olaparib when having sexual intercourse with a pregnant woman or with a woman of childbearing potential. Female partners of male patients should also

use a highly effective form of contraception (as described in Appendix V) if they are of childbearing potential. Male patients should not donate sperm throughout the period of taking olaparib and for 3 months following the last dose of olaparib.

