- 3.29r Co-morbid systemic illnesses or other severe concurrent disease which, in the judgment of the investigator, would make the patient inappropriate for entry into this study or interfere significantly with the proper assessment of safety and toxicity of the prescribed regimens. Patients considered a poor medical risk due to a serious, uncontrolled medical disorder, non-malignant systemic disease or active, uncontrolled infection. Examples include, but are not limited to, uncontrolled ventricular arrhythmia, recent (within 3 months) myocardial infarction, uncontrolled major seizure disorder, unstable spinal cord compression, superior vena cava syndrome, extensive interstitial bilateral lung disease on High Resolution Computed Tomography (HRCT) scan or any psychiatric disorder that prohibits obtaining informed consent.

- 3.29s Immunocompromised patients and patients known to be HIV serologically positive and currently receiving antiretroviral therapy.

NOTE: Patients known to be HIV positive, but without clinical evidence of an immunocompromised state, are eligible for this trial.

- 3.29t Receiving any other investigational agent which would be considered as a treatment for the primary neoplasm.

- 3.29u Previous and/or intercurrent cancers. With the exception of: curatively-treated cancers with no recurrence in ≥ 5 years or early cancers treated with curative intent, including but not limited to cervical carcinoma in situ, superficial, noninvasive bladder cancer, basal cell carcinoma, squamous cell carcinoma in situ, , , ductal carcinoma in situ (DCIS), Stage 1, grade 1 endometrial carcinoma, or endoscopically resected gastrointestinal cancers limited in mucosal layer.

NOTE: All cancer treatments for cancers that were distinct in a primary site other than biliary tract cancer must be completed ≥ 3 years prior to registration.

- 3.29v Pleural effusion or ascites that causes respiratory compromise (\geq CTCAE v5.0 Grade 2 dyspnea).

- 3.29w Previous enrollment in the present study

- 3.29x Prior exposure to any PARP inhibitor including olaparib.

- 3.29y Known hypersensitivity reaction to olaparib or any of the excipients of the product.

- 3.29z Myelodysplastic syndrome/acute myeloid leukemia or with features suggestive of MDS/AML.

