 5. Hematology and chemistry tests to be done prior to each cycle. Activated partial thromboplastin time (APTT) will be performed at screening and if clinically indicated. International normalized ratio (INR) will be performed at screening and if clinically indicated. Each coagulation test result will be recorded in CRF. In case a patient shows an AST or ALT $\geq 3 \times$ ULN together with total bilirubin $\geq 2 \times$ ULN please refer to Appendix 'Actions required in cases of increases in liver biochemistry and evaluation of Hy's Law' for further instructions.
 6. If patient goes off study during Cycle 1 and last CT scan was done > 28 days prior, the CT scan must be done.
 7. If baseline history, exam, weight, ECOG PS, and blood pressure were performed ≤ 3 days of Cycle 1 Day 1, they do not need to be repeated for Cycle 1 Day 1.
 8. Archival tissue will be collected ≤ 28 after registration. Patients may initiate study treatment prior to the receipt of the archival tissue. See section 17.
 9. Optional tissue collection at end of treatment.
 10. At the time of radiographic assessment (Every 8 weeks).
- R Research funded.

5.0 Stratification Factors OR Grouping Factor:

None

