7.0 Protocol Treatment

7.1 Treatment Schedule - Use actual weight or estimated dry weight if fluid retention

Agent	Dose	Route	Frequency	ReRx
Olaparib	300mg (Starting dose)	PO	Twice Daily (28 day cycle)	Every 28 days

The planned dose of 300 mg taken twice a day will be made up of two (2) x 150 mg tablets, with 100 mg tablets used to manage dose reductions. The planned dose should be taken at the same times in the morning and evening of each day, approximately 12 hours apart with approximately 240 mL of water. The olaparib tablets should be swallowed whole and not chewed, crushed, dissolved or divided. Olaparib tablets can be taken with or without food.

If vomiting occurs shortly after the olaparib tablets are swallowed, the dose should only be replaced if all of the intact tablets can be seen and counted. Should any patient enrolled on the study miss a scheduled dose for whatever reason (e.g. as a result of forgetting to take the tablets or vomiting), the patient will be allowed to take the scheduled dose up to a maximum of 2 hours after that scheduled dose time. If greater than 2 hours after the scheduled dose time, the missed dose is not to be taken and the patient should take their allotted dose at the next scheduled time.

7.2 Patients can be instructed in administration techniques and granted treatment independence with nursing staff approval.

7.3 For this protocol, the patient must return to the consenting ACCRU institution for evaluation at least every 28 days +/- 7 days during treatment.

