If new or worsening pulmonary symptoms (e.g. dyspnea) or radiological abnormality occurs, an interruption in study treatment dosing is recommended and a diagnostic workup (including a high resolution CT scan) should be performed, to exclude pneumonitis. Following investigation, if no evidence of abnormality is observed on CT imaging and symptoms resolve, then study treatment can be restarted, if deemed appropriate by the investigator. If significant pulmonary abnormalities are identified, these need to be discussed with the Principal Investigator.

Renal impairment

If subsequent to study entry and while still on study therapy, a patient's estimated CrCl falls below the threshold for study inclusion (≥ 51 ml/min), retesting should be performed promptly.

A dose reduction is recommended for patients who develop moderate renal impairment (calculated creatinine clearance by Cockcroft-Gault equation or based on a 24 hour urine test of between 31 and 50 ml/min) for any reason during the course of the study: the dose of olaparib should be reduced to 200 mg twice daily.

Because the CrCl determination is only an estimate of renal function, in instances where the CrCl falls to between 31 and 50 mL/min, the investigator should use his or her discretion in determining whether a dose change or discontinuation of therapy is warranted.

Olaparib has not been studied in patients with severe renal impairment (creatinine clearance ≤ 30 ml/min) or end-stage renal disease; if patients develop severe impairment or end stage disease it is recommended that olaparib be discontinued.

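### As the text reads, inclusion criterion 3.17 admits creatinine clearance of 1 mL/min or more, while section 8.2 gives the inclusion threshold as 51 mL/min or more

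*Combined protocol and SAP*

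**What the plan says.** Among the laboratory values required within 7 days before registration, criterion 3.17 lists "Creatinine clearance estimated of ≥ 1 mL/min using the Cockcroft-Gault equation" and prints the formula for each sex. The same list has "Serum creatinine $\leq 1.5 \times$ ULN".

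The renal impairment part of section 8.2 treats the entry limit as a different number. It asks for prompt retesting when clearance on study "falls below the threshold for study inclusion (≥ 51 ml/min". It then recommends 200 mg twice daily at 31 to 50 mL/min, leaving the investigator discretion over a dose change or discontinuation. At 30 mL/min or below it states that olaparib has not been studied and recommends stopping.

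Two exclusions bear on renal function. Criterion 3.29g covers "Renal failure requiring hemo-or peritoneal dialysis". Criterion 3.29r covers severe concurrent disease that, "in the judgment of the investigator, would make the patient inappropriate for entry into this study". Section 7.1 gives one starting dose: "The planned dose of 300 mg taken twice a day".

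**The concern.** Both statements describe the same entry limit, and they differ by a factor of 51. A site that applies 3.17 literally would register patients whom 8.2 assumes are not in the trial. The registration application verifies eligibility (6.22), but if it checks against 3.17 as worded it would not catch them.

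The stake is dosing safety. A patient could start at 300 mg twice daily with a clearance at which 8.2 recommends a lower dose, or at which it says the drug has not been studied. The threshold also forms part of the definition of eligibility in 13.1, so its value should not be in doubt.

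**Working it through.** **Step 1. Compare the two statements.** 3.17 gives 1 mL/min; 8.2 gives 51 mL/min and calls it the inclusion threshold. The bands in 8.2 (31 to 50, then 30 and below) begin just under 51. They fit an entry limit of 51 and do not fit a limit of 1.

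**Step 2. Does the serum creatinine limit stand in for a clearance limit of 51?** By the 3.17 formula, CrCl = K / creatinine, with K = (140 − age) x weight / 72, multiplied by 0.85 for women. For a woman of 70 years and 60 kg, K = 70 x 60 x 0.85 / 72 = 49.58. The documents give no ULN. I assume 1.0 to 1.3 mg/dL, so the creatinine limit is 1.50 to 1.95 mg/dL. Ages and weights are illustrative.

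| Patient | K | Creatinine at which CrCl = 51 (K/51) | CrCl at the creatinine limit, ULN 1.0 to 1.3 |
|---|---|---|---|
| Woman 80 y, 50 kg | 35.42 | 0.69 | 23.6 to 18.2 |
| Woman 70 y, 60 kg | 49.58 | 0.97 | 33.1 to 25.4 |
| Woman 60 y, 60 kg | 56.67 | 1.11 | 37.8 to 29.1 |
| Man 70 y, 75 kg | 72.92 | 1.43 | 48.6 to 37.4 |
| Man 60 y, 75 kg | 83.33 | 1.63 | 55.6 to 42.7 |
| Man 50 y, 80 kg | 100.00 | 1.96 | 66.7 to 51.3 |

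The first four can fall below 51 within the creatinine limit at every assumed ULN. The fifth can do so only if the ULN exceeds 1.634 / 1.5 = 1.09. The sixth cannot in this range.

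**Step 3. How often could clearance be 30 or below?** This needs creatinine of at least K/30. For the woman of 80 that is 1.18 mg/dL, inside the limit at every assumed ULN. For the woman of 70 it is 1.65 (ULN about 1.10 or more), and for the woman of 60 it is 1.89 (ULN about 1.26 or more). For the three men it is 2.43, 2.78 and 3.33, all above the highest assumed limit of 1.95.

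**Step 4. Does a floor of 1 mL/min do anything?** Clearance equals 1 when creatinine equals K, that is 35 to 100 mg/dL for these patients. The creatinine limit excludes them long before that, so the clearance line as it reads has no effect.

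**Step 5. Do the exclusions close the gap?** 3.29g stops only patients on dialysis. 3.29r leaves the decision to the investigator and gives no cut-off.

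**Step 6. After correction.** With 51 in 3.17, nobody newly entering falls in the 8.2 reduction band, and the two sections agree.

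**The case against.** The strongest reply is that the plan may contain no error. The text was read from PDF by a program, and one character separates 1 from 51. The secondary goals run 2.21, 2.22, 2.23 and then "2.2 To assess the duration of response for patients with advanced biliary tract cancer", followed by 2.25, so a digit is missing there too. That possibility stands, and the extracted text cannot settle it. Nor is it shown: the document has slips that look like source errors, such as a section numbered 16.354, a second section 14.4, and citations of an Appendix V when the appendices end at IV.

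It is also fair that 8.2 itself supplies the intended value, and that safeguards exist. Section 4.0 requires "Hematology and chemistry tests to be done prior to each cycle", and an investigator who reads 8.2 would see 51. These let a careful site notice and act. They do not make 51 an entry criterion.

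A reader might infer three stronger things, none of which the documents support:

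- That section 7.1 is defective for lacking a renally adjusted starting dose. With entry at 51 or above, no patient starts in the reduction band, and a single starting dose is coherent.
- That 8.2 must be reworded because it addresses impairment that develops on study. Once 3.17 reads 51, that wording covers everyone who can newly enter.
- That the trial's design or primary analysis is compromised. The Simon boundaries and error rates in 16.2 do not depend on this criterion.

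**Conclusion.** The contradiction is real in the text as it reads, and no other entry rule removes it. If 3.17 does say 1 in the source file, patients can be registered and started at 300 mg twice daily at clearances for which 8.2 recommends reducing or stopping olaparib. For older or lighter patients this can happen at creatinine values within the allowed limit. Entry at 30 mL/min or below is possible but needs a narrower set of patients.

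The sizes rest on an assumed ULN of 1.0 to 1.3 mg/dL and on illustrative ages and weights. The documents do not show how many such patients would enrol. It would go too far to conclude that the sponsor meant to admit patients with severe renal impairment: 8.2 points clearly to 51 as the intended value. Confidence that the source contains the error is low, because a lost digit would explain it equally well. The point is one of eligibility and dosing safety and has no bearing on sample size, decision rules or estimation.

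**What to change.** Look at 3.17 in the source file. If it reads 51 mL/min, nothing needs to change.

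If it reads 1 mL/min:

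1. Correct it prospectively to 51 mL/min, the value 8.2 already states.
2. Calculate baseline clearance for patients already on treatment, and apply the 8.2 dosing recommendations, with their investigator discretion, to any below 51. Do not reclassify patients already registered as ineligible for the primary analysis in 16.21.

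The cost is one look at a file and, if needed, one number in an amendment plus a calculation for at most 36 patients from age, weight and creatinine already collected. No new tests are needed, and 7.1, 8.2 and the statistical section stay as they are.

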9.0 Ancillary Treatment/Supportive Care

- 9.1 Antiemetic's may be used at the discretion of the attending physician.
- 9.2 Blood products and growth factors should be utilized as clinically warranted and following institutional policies and recommendations. The use of growth factors should follow published guidelines of the American Society of Clinical Oncology (ASCO) Recommendations for the Use of WBC Growth Factors: American Society of Clinical Oncology Clinical Practice Guideline Update. J Clin Oncol 2015;33:3199-3212.
- 9.3 Patients should receive full supportive care while on this study. This includes blood product support, antibiotic treatment, and treatment of other newly diagnosed or concurrent medical conditions. All blood products and concomitant medications such as antidiarrheals, analgesics, and/or antiemetics received from the first day of study

treatment administration until 30 days after the final dose will be recorded in the medical records.

- 9.4 Diarrhea: This could be managed conservatively with loperamide. The recommended dose of loperamide is 4 mg at first onset, followed by 2 mg every 2-4 hours until diarrhea free (maximum 16 mg/day).

In the event of grade 3 or 4 diarrhea, the following supportive measures are allowed: hydration, octreotide, and antidiarrheals.

If diarrhea is severe (requiring intravenous rehydration) and/or associated with fever or severe neutropenia (grade 3 or 4), broad-spectrum antibiotics must be prescribed. Patients with severe diarrhea or any diarrhea associated with severe nausea or vomiting **should be hospitalized** for intravenous hydration and correction of electrolyte imbalances.

- 9.5 Concomitant Medications

The following medications below are to be avoided while on study:

Restricted concomitant medications

Medication/class of drug:	Usage (including limits for duration permitted and special situations in which it's allowed):

Strong CYP3A inhibitors: itraconazole, telithromycin, clarithromycin, boosted protease inhibitors, indinavir, saquinavir, nelfinavir, boceprevir, telaprevir
 
Moderate CYP3A inhibitors: ciprofloxacin, erythromycin, diltiazem, fluconazole, verapamil
	
Strong or moderate CYP3A inhibitors should not be taken with olaparib. If there is no suitable alternative concomitant medication then the dose of olaparib should be reduced for the period of concomitant administration. The dose reduction of olaparib should be recorded in the CRF with the reason documented as concomitant CYP3A inhibitor use.
 
 Strong CYP3A inhibitors – reduce the dose of olaparib to 100 mg twice daily for the duration of concomitant therapy with the strong inhibitor and for 5 half-lives afterwards. Moderate CYP3A inhibitors - reduce the dose of olaparib to 150 mg twice daily for the duration of concomitant therapy with the moderate inhibitor and for 3 half-lives afterwards. After the washout of the inhibitor is complete, the olaparib dose can be re-escalated.

Strong inducers: phenobarbital, phenytoin, rifampicin, rifabutin, rifapentine, carbamazepine, nevirapine, enzalutamide and St John's Wort
 
Moderate CYP3A inducers: bosentan, efavirenz and modafinil
	
Strong or moderate CYP3A inducers should not be taken with olaparib. If the use of any strong or moderate CYP3A inducers are considered necessary for the patient's safety and welfare this could diminish the clinical efficacy of olaparib.
 
If a patient requires use of a strong or moderate CYP3A inducer then they must be monitored carefully for any change in efficacy of olaparib

Restricted concomitant medications

Medication/class of drug:	Usage (including limits for duration permitted and special situations in which it's allowed):

 • CYP3A4 substrates: hormonal contraceptive, simvastatin, cisapride, cyclosporine, ergot alkaloids, fentanyl, pimozone, sirolimus, tacrolimus and quetiapine • CYP2B6 substrates: bupropion, efavirenz • OATP1B1 substrates: bosentan, glibenclamide, repaglinide, statins and valsartan • OCT1, MATE1 and MATE2K substrates: metformin • OCT2 substrates: serum creatinine • OAT3 substrates: furosemide, methotrexate 	
Effect of olaparib on other drugs
 
Based on limited in vitro data, olaparib may increase the exposure to substrates of CYP3A4, OATP1B1, OCT1, OCT2, OAT3, MATE1 and MATE2K.
 
Based on limited in vitro data, olaparib may reduce the exposure to substrates of 2B6.
 
Caution should be observed if substrates of these isoenzymes or transporter proteins are co-administered.

Anticoagulant therapy	
Patients who are taking warfarin may participate in this trial; however, it is recommended that international normalized ratio (INR) be monitored carefully at least once per week for the first month, then monthly if the INR is stable. Subcutaneous heparin and low molecular weight heparin are permitted.

Palliative radiotherapy	
Palliative radiotherapy may be used for the treatment of pain at the site of bony metastases that were present at baseline, provided the investigator does not feel that these are indicative of clinical disease progression during the study period. Study treatment should be discontinued for a minimum of 3 days before a patient undergoes therapeutic palliative radiation treatment. Study treatment should be restarted within 4 weeks as long as any bone marrow toxicity has recovered.

Administration of other anti-cancer agents	
Patients must not receive any other concurrent anti-cancer therapy, including investigational agents, while on study treatment. Patients may continue the use of bisphosphonates or denosumab for bone disease and corticosteroids for the symptomatic control of brain metastases provided the dose is stable before and during the study and they were started at least 4 weeks prior to beginning study treatment.

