8.0 Dosage Modification Based on Adverse Events

Any toxicity observed during the course of the study could be managed by interruption of the dose of study treatment or dose reductions. Repeat dose interruptions are allowed as required, for a maximum of 4 weeks on each occasion. If the interruption is any longer, the study team must be informed. Study treatment can be dose reduced to 250 mg twice daily as a first step and to 200 mg twice daily as a second step. If the reduced dose of 200 mg twice daily is not tolerable, no further dose reduction is allowed and study treatment should be discontinued.

Once dose is reduced, escalation is not permitted.

ALERT: ADR reporting may be required for some adverse events (See Section 10)

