Study treatment dose interruption for conditions other than toxicity resolution should be kept as short as possible. If a patient cannot restart study treatment within 4 weeks for resolution of intercurrent conditions not related to disease progression or toxicity, the case should be discussed with Principal Investigator.

All dose reductions and interruptions (including any missed doses), and the reasons for the reductions/interruptions are to be recorded in the eCRF. Study treatment should be stopped at least 3 days prior to planned surgery. After surgery study treatment can be restarted when the wound has healed. No stoppage of study treatment is required for any biopsy procedure.

Study treatment should be discontinued for a minimum of 3 days before a patient undergoes radiation treatment. Study treatment should be restarted within 4 weeks as long as any bone marrow toxicity has recovered.

Repeat dose interruptions are allowed as required, for a maximum of 4 weeks on each occasion. If the interruption is any longer than this the study monitor must be informed. Where toxicity reoccurs following re-challenge with study treatment, and where further dose interruptions are considered inadequate for management of toxicity, then the patient should be considered for dose reduction or must permanently discontinue study treatment.

Study treatment can be dose reduced to 250 mg twice daily as a first step and to 200 mg twice daily as a second step. Treatment must be interrupted if any NCI-CTCAE grade 3 or 4 adverse event occurs which the investigator considers to be related to administration of study treatment. Excludes alopecia, non-refractory nausea/vomiting, non-refractory hypersensitivity and nonclinical and asymptomatic laboratory abnormalities.

Study treatment should be stopped at least 3 days prior to planned surgery. After surgery study treatment

can be restarted when the wound has healed. No stoppage of study treatment is required for any needle biopsy procedure.

Study treatment should be discontinued for a minimum of 3 days before a patient undergoes radiation treatment. Study treatment should be restarted within 4 weeks as long as any bone marrow toxicity has recovered.

Because the adverse effects related to olaparib may include asthenia, fatigue and dizziness, patients should be advised to use caution while driving or using machinery if these symptoms occur.

Management of new or worsening pulmonary symptoms

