Absorption: Rapid; delayed with a high-fat meal (extent of absorption not significantly altered).
Time to peak: Capsule: 1-3 hours; tablet: 1.5 hours
Bioavailability: Tablet formulation has higher bioavailability than the capsule formulation
Distribution: Capsule: 167 liters; tablet: 158 liters
Metabolism: Primarily hepatic via CYP3A4; the majority of metabolism is through oxidation with some metabolites undergoing subsequent glucuronide or sulfate conjugation
Half-life elimination: Capsule: 11.9 hours; tablet: 14.9 hours
Protein binding: ~82%
Excretion: Urine (44%, mostly metabolites); feces (42%, mostly metabolites)
- 15.16 **Potential Drug Interactions:**
CYP3A4/5 are the isozymes predominantly responsible for the metabolic

clearance of olaparib. Clinical studies conducted with a tablet formulation to evaluate the impact of known CYP3A inhibitors and inducers have shown that co-administration of a potent CYP3A inhibitor, itraconazole, increased olaparib C_{max} by 142% and increased mean AUC by 270% and that co-administration of a potent CYP inducer, rifampicin, decreased C_{max} by 71% and mean AUC by 87%. Moderate inhibitors and inducers of CYP3A are also predicted to significantly alter the exposure of olaparib. It is therefore recommended that known strong CYP3A inhibitors (eg, itraconazole, telithromycin, clarithromycin, boosted protease inhibitors, indinavir, saquinavir, nelfinavir, boceprevir, telaprevir) or moderate CYP3A inhibitors (ciprofloxacin, erythromycin, diltiazem, fluconazole, verapamil) should not be taken with olaparib.

Strong (eg, phenobarbital, phenytoin, rifampicin, rifabutin, rifapentine, carbamazepine, nevirapine, enzalutamide and St John's Wort) and moderate CYP3A inducers (eg, bosentan, efavirenz, modafinil) of CYP3A should not be taken with olaparib.

Caution should be exercised when substrates of CYP3A4 are combined with olaparib, in particular those with a narrow therapeutic margin (eg, simvastatin, cisapride, cyclosporine, ergot alkaloids, fentanyl, pimozide, sirolimus, tacrolimus and quetiapine). Substrates of UGT1A1 should also be given with caution in combination with olaparib (eg, irinotecan, nintedanib, ezetimibe, raltegravir or buprenorphine).

Induction of CYP1A2, 2B6 and 3A4 has been shown in vitro with CYP2B6 being most likely to be induced to a clinically relevant extent. It cannot be excluded that olaparib upon co-administration may reduce the exposure to substrates of these metabolic enzymes.

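### Section 9.5 sets olaparib at 100 mg twice daily with any strong CYP3A inhibitor; for a patient already at 200 mg, the protocol's own itraconazole figure implies a higher AUC than the assigned dose (about 135% or 185%)

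*Combined protocol and SAP*

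**What the plan says.** Section 9.5 says strong CYP3A inhibitors should not be taken with olaparib. If there is no suitable alternative, the site is to "reduce the dose of olaparib to 100 mg twice daily for the duration of concomitant therapy with the strong inhibitor" and for 5 half-lives afterwards. The row does not mention the patient's current dose level. It adds: "The dose reduction of olaparib should be recorded in the CRF with the reason documented as concomitant CYP3A inhibitor use". On recovery: "After the washout of the inhibitor is complete, the olaparib dose can be re-escalated".

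A patient can already be at 200 mg twice daily by two routes. In Section 8.0, 200 mg is the second and last step for toxicity: "If the reduced dose of 200 mg twice daily is not tolerable, no further dose reduction is allowed and study treatment should be discontinued". In Section 8.2 (Renal impairment), a fall in creatinine clearance to 31–50 mL/min calls for a reduction "for any reason during the course of the study: the dose of olaparib should be reduced to 200 mg twice daily", subject to investigator discretion. Section 8.0 also states: "Once dose is reduced, escalation is not permitted".

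The only effect size for a strong inhibitor is in Section 15.16. With the tablet, itraconazole increased olaparib Cmax "by 142% and increased mean AUC by 270" per cent. Itraconazole is also the first drug on the Section 9.5 list of strong inhibitors.

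**The concern.** A fixed dose of 100 mg is a two-thirds cut from 300 mg but only a halving from 200 mg. If the inhibitor multiplies AUC by more than 2, the instructed reduction leaves a 200 mg patient with more exposure than before. These patients are at 200 mg because they did not tolerate more or because renal function fell, and those reduced for toxicity have no further step down. A site could follow Section 9.5 exactly and partly undo that reduction.

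Routine blood tests are scheduled for Day 1 of each 28-day cycle (Section 4.0), so a short inhibitor course could fall between draws. Interruption for related grade 3 or 4 events (Section 8.2) acts only once harm has appeared.

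**Working it through.** The protocol states no exposure after the adjustment, so there is no figure of its own to reproduce first.

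**Inputs.** Dose with a strong inhibitor: 100 mg twice daily (9.5). Possible assigned doses D: 300, 250 or 200 mg twice daily (8.1). AUC multiplier R for itraconazole, from the 270% in 15.16: 2.7 if a ratio, 3.7 if an increase. Assumptions not stated in the documents: AUC scales as dose^b, with b = 1 for proportionality; other strong inhibitors act like itraconazole.

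**Formula.** AUC as a percentage of that at the assigned dose = 100 × R × (100/D)^b.

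| Assigned dose D | R = 2.7, b = 1 | R = 3.7, b = 1 |
|---|---|---|
| 200 mg | 100 × 2.7 × 0.5 = 135% | 100 × 3.7 × 0.5 = 185% |
| 250 mg | 100 × 2.7 × 0.4 = 108% | 100 × 3.7 × 0.4 = 148% |
| 300 mg | 100 × 2.7 / 3 = 90% | 100 × 3.7 / 3 = 123% |

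**Sensitivity to dose proportionality, D = 200.** At b = 1.2, 2^1.2 = 2.30, giving 2.7/2.30 = 118% or 3.7/2.30 = 161%. Break-even b = ln R / ln 2: ln 2.7 / ln 2 = 1.43, or ln 3.7 / ln 2 = 1.89. If AUC rises less than proportionally with dose (b below 1), the excess is larger, because 2^b is smaller.

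**Sensitivity to the inhibitor, D = 200, b = 1.** An excess needs more than a 2.0-fold rise. As a share of itraconazole's AUC increase this is (2.0 − 1)/(R − 1): 1/1.7 = 59% on the ratio reading, 1/2.7 = 37% on the increase reading. For itraconazole itself no class assumption is needed.

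**Matching dose.** The dose giving the AUC of 200 mg alone is 200/2.7 = 74 mg or 200/3.7 = 54 mg twice daily. Neither can be made up. The smallest tablet is 100 mg (15.12), tablets may not be divided (7.1), and 50 mg capsules may not be exchanged mg-per-mg (15.14).

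**Cmax, D = 200, b = 1.** 1.42/2 = 71% on the ratio reading, 2.42/2 = 121% on the increase reading. The direction is unknown.

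**The case against.** The strongest reply is that the excess is conditional and the situation rare. Dose proportionality and class similarity are assumptions, and the break-even values do not show which side the truth lies on. Section 15.0 refers sites to the package insert, which cannot be checked here. Strong inhibitors are excluded at entry with a 2-week washout (3.29aa), are to be avoided on study, and are dosed around only when there is no alternative. Staff are told to review medication lists for interactions (15.19b3). A hold also replaces reduced-dose treatment with none in metastatic disease.

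Much of this stands. It limits the reach and makes the percentages conditional. It does not remove the gap: Section 9.5 expressly provides for this use, names itraconazole, and gives a number that ignores the current dose.

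Four stronger readings are tempting, and the documents do not support them.

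- *The 100 mg rule overexposes every patient, even beyond the maximum tolerated dose of 300 mg in Section 10.0.* That follows only on the increase reading (370 mg-equivalent, 123% at 300 mg). On the ratio reading a 300 mg patient is at 90%. The wording of 15.16 favours an increase, since the rifampicin figures in the same sentence are plainly changes, but this does not settle it. For the same reason, 100 mg cannot be declared right at 300 mg until the figure is clarified.
- *The CRF would hide the problem.* The reason must be recorded as inhibitor use, so the episodes can be identified.
- *Sections 8.0 and 9.5 contradict each other on re-escalation, so a 200 mg patient could go back to 300 mg.* The no-escalation sentence opens Section 8 without qualification, and the renal text lies inside that section. Re-escalation in 9.5 most naturally means undoing the inhibitor step. Naming the level would be a wording clarification only.
- *Moderate inhibitors share the fault.* The documents give no effect size for them.

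**Conclusion.** The point holds for patients already at 200 mg twice daily. Section 9.5 gives them 100 mg with any strong inhibitor, and the protocol's itraconazole figure then implies an AUC of about 135% (ratio) or 185% (increase) of that at 200 mg. Confidence is high that 9.5 does not address these patients. It is moderate for the percentages, which rest on the two assumptions above. The claim is about AUC only.

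Severity is minor. A patient must already be at 200 mg and then need a strong inhibitor with no suitable alternative, among at most 36 patients. The two-stage design and its error rates are not affected.

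**What to change.** In Section 9.5, add for patients at 200 mg: hold olaparib during an unavoidable strong inhibitor and its 5-half-life washout, unless the sponsor and drug supplier specify another dose, then resume at 200 mg. A hold is the workable default because no smaller tablet step exists. It can be handled under the existing Section 8.2 text on interruptions not due to toxicity, which keeps them as short as possible and refers longer ones to the Principal Investigator: "If a patient cannot restart study treatment within 4 weeks for resolution of intercurrent conditions".

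Ask the supplier whether the 270% in 15.16 is an increase or a ratio, state the answer there (and likewise for the 142%), and confirm the dose with a strong inhibitor at 250 mg and 300 mg accordingly.

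The cost is a short amendment to one table row in 9.5, a clarification in 15.16 and one supplier query. It adds no patients, visits or procedures. The downside is a short interruption in very few patients. The documents give no inhibitor half-lives. For an assumed 6 to 36 hours, 5 half-lives add 5 × 6 h = 1.25 days to 5 × 36 h = 7.5 days, so an inhibitor course of up to 28 − 7.5 = 20.5 to 28 − 1.25 = 26.75 days stays within 4 weeks. A hold before the first scan could affect that patient's primary-endpoint result, so the hold and its reason should be recorded in the CRF.
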